Study Protocol

Official Title of the study: Effectiveness and safety of Chinese herbal medicine for hepatitis B virus-related acute-on-chronic liver failure: A multi-center, randomized and controlled trial

NCT number: not yet assigned

Date of the document: June 21, 2018

This prospective, multi-center, parallel, centrally randomized controlled trial was designed in accordance with the Consolidated Standards of Reporting Trials (CONSORT) and Standard Protocol Items: Recommendations for Interventional Trials (SPIRIT) guideline, which is led by the principal investigator from 302 military hospital in Beijing, will be carried out from September 2018 and December 2020 among 16 tertiary academic hospitals in China. Patients with hepatitis B virus (HBV) related Acute-on-chronic liver failure (ACLF) will be randomly allocated to the Chinese herbal medicine (CHM) group or the standard medical treatment (SMT) group in a 1:1 ratio. The last patient will be enrolled before August 2019 to make sure the availability of 48 week's survival status by the end of this study. We will decide whether to expand additional institutions to guarantee adequate enrolments after interim assessment of effective participant numbers around December 2018. Patients in the SMT group will receive the standard medical treatment, and patients in the CHM group will receive rhubarb decoction enema for 1 week and CHM for 8 weeks additionally. All patients will be followed at pre-designed time points after 8 weeks' observational period until August 30, 2020 for the primary outcome and secondary outcomes.

The study is consistent with Good Clinical Practice(GCP) guidelines and has been approved by 302 military hospital ethics review committee (2018007D). Written informed consent is requisite to be signed by the patients or the authorized person under the willingness. The privacy and data of all participants will be protected carefully before, during and after the trial.

Patients will be consented and enrolled by co-principal investigators at each institution and managed by care providers including residents, attending physicians and nurses according to the protocol. Most of the patients will be treated in hospital for 8 weeks so clinicians can supervise the administration of CHM, in addition, the policy of reimbursement filed by the lab results at determined time points will boost the regular follow-up of this study.

Diagnostic criteria

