The diagnosis of HBV-ACLF refers to the guideline of liver failure issued by Chinese Group on the Study of Severe Hepatitis B (COSSH) in 2012. In this guideline, HBV-ACLF was described as acute decompensation of liver function within short time (28 days usually) in patients with previously diagnosed or undiagnosed chronic liver disease, reaching the following obligatory criteria: (1) asthenia combined with obvious symptoms of digestive tract, (2) quick progress of jaundice defined as total bilirubin (TBIL) greater than 10 mg/dl or increase 1mg/dl daily, (3) coagulopathy with prothrombin activity less than or equal to 40% or international normalized ratio (INR) greater or equal to 1.5 except other extrahepatic reasons and another dispensable item of decompensated ascites and/or hepatic encephalopathy. There are three grades classified by the degree of coagulopathy and liver complications.

The TCM syndrome was judged by two qualified senior TCM physicians simultaneously based on the published criteria to decide what CHM will be given, and the discrepancy will be solved by consulting another senior physician.

Inclusion criteria

(1) In-patients with ACLF. (2) Patients with chronic hepatitis B or compensated cirrhosis caused by HBV. (3) Patients who are willing to sign the informed consent. (4) Patients aged from 16 to 65 years old.

Exclusion criteria

(1) Acute liver failure, sub-acute liver failure, or chronic liver failure. (2) ACLF caused by another disease such as autoimmune disorder, drug, alcohol, toxin, parasites other than HBV. (3) Pregnant or lactating women. (4) Primary liver cancer. (5) Combined with other severe systemic diseases or mental disease. (6) Anti-HIV positive or combined with infection of hepatitis A, C, D, E virus or cytomegalovirus, Epstein-Barr virus. (7) Patients participating in other clinical trials three months back. (8) Patients unwilling to cooperate. (9) Poor compliance, unable to guarantee to complete the protocol. (10) Complicated by severe cerebral edema, severe infection, type I hepatorenal syndrome (HRS), and gastrointestinal hemorrhage. (11) Patients allergic to one of the Chinese herbs in this protocol.

Criteria for discontinuing or modifying allocated interventions

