The study will end at once if severe adverse events associated with CHM occurs or sufficient evidence indicates that adding CHM is not superior to the SMT group. Besides, CHM will discontinue and the final status will be censored in the condition of liver transplantation or the onset of liver cancer. Allocated interventions can be changed upon participant's request. All these changes will be recorded and analyzed based on intention-to-treat (ITT).

Intervention

Standard medical treatment

The SMT include a high-calorie diet; nucleoside analogues for HBV DNA-positive patients; sodium restriction, diuretics and paracentesis combined with albumin infusion for ascites; lactulose and L-ornithine aspartate and lactulose for HE and hyper-ammonia; hemostatic treatment for gastrointestinal hemorrhage; antibiotics for infections and renal replacement for HRS and uremic symptoms. CHM formulas, whatever routes of administration, are prohibited in the SMT group.

Chinese herbal medicine formula

There are two kinds of CHM based on traditional Chinese Medicines (TCM) syndromes. The common components of the two CHM formulas include *Artemisiacapillaris* Thunb (30g), *Salvia miltiorrhiza* Bge (30g), *Rhizoma*

Atractylodis Macrocephalae (30g), Rubia cordifolia L (30g), Sieyesbeckiaorientalis L (30g). Additional four components of Paeoniae Radix Rubra (60g), Gardenia jasminoides Ellis (9g), Hedyotis diffusa Willd (30g), Bletilla striata (15g) are involved for excess syndrome, and five other components of Astragalus membranaceus (30g), Radix Pseudostellariae (15g), Radix Aconiti Lateralis Praeparata (10g), Galli Gigeriae Endothelium Corneum (20g), Polygonum cuspidatum Sieb.et Zucc (15g) are involved for deficiency syndrome. All ingredients are manufactured as a Chinese herbal granule in a specific weight ratio to the raw herb (Beijing Kang Rentang Pharmaceutical Co., Ltd, Beijing, China) in accordance with the quality criteria of Chinese pharmacopoeia in 2015. Patients will take one dosage of CHM granule per day for 8 weeks. For patients who cannot take oral medicine can be switched to colon route by the colonic therapy system (IMS-100A produced by Sunny Medical in Beijing China).

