In addition, patients in the CHM group will also receive daily herbal enema of 100 microliter decoction composed by Radix et Rhizoma Rhei Palmati (Dahuang) 30g and Fructus Mume (Wumei) 30g for 7 days expect the following contraindications: (1) severe hemorrhoid, (2) female patients during menstruation, (3) anal stenosis, (4) artificial anal and (5) cardiac disease.

Outcome measurements

Primary outcome

The primary outcome is transplant-free survival at week 12.

Secondary outcomes

Secondary outcomes include (1) transplant-free survival at week 24, (2) the influence on liver function assessed by MELD score (involving levels of serum bilirubin, creatinine, INR and sodium) at week 12, (3) the influence on liver function assessed by Child-Pugh score (involving the serum bilirubin, coagulation function, albumin and the complication of hepatic encephalopathy and ascites) at week 12. (4) quality of life assessed by WHOQOL-BRIEF at week 12 and (5) the incidence of serious complications (including infections, encephalopathy, HRS, and gastrointestinal bleeding) from week 1 to week 24.

Safety outcomes

Primary vital signs, physical examinations, electrocardiogram and some laboratory tests such as routine blood test, urine test, renal function will be assessed before and after treatment to monitor the safety of this study. Furthermore, adverse events are also recorded in a predesigned case report form (CRF) through the whole study period. An independent safety committee will analyze the incidence and severity of adverse events to identify any unexpected adverse events or mortality in the CHM groups.

Other assessed parameters

Epidemiological characteristics, the details of nucleoside/nucleotide analog therapy, family history of liver disease were collected from patient medical record, the level of HBV DNA, endotoxin, and lymphocyte subsets were tested as well as CLIP-C-ACLF score were computed at week 24 and 48. The plasma level of HBV DNA, endotoxin, and cytokines were tested in ADICO clinical laboratories (Shanghai, China) which is blind to the allocation information. Remnant plasma will be stored at -80°C for ancillary studies. Women of childbearing age will undergo pregnancy test for the eligibility.

Sample size

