The proposed -12% superiority margin of 8-week mortality rate was chosen based on our previous results of 30.87% in the SMT group. Considering a power of 0.80 and 10% of attrition rate, 255 subjects are needed for each group to achieve the significance level of 0.05 in assessing the difference between the two groups.

Randomization

The eligible patients will be randomly allocated to the SMT group and CHM group in a 1:1 ratio. The sealed numbers are generated by a computerized random number generator with statistical analysis system (SAS) software by an independent statistician from the center of clinical evaluation in China Academy of Chinese medical sciences (Beijing, China) and are concealed using opaque envelopes.

Trial monitoring

Trial monitoring is assumed by an independent Contract Research Organization so as to verify that: (1) The rights and well-being of human subjects are protected. (2) The reported trial data are accurate, complete, and verifiable from source documents. (3) The conduct of the trial is in compliance with the currently approved protocol/amendment(s), with GCP, and with the applicable regulatory requirement(s). Monitors should be appropriately trained and have the scientific and/or clinical knowledge needed to monitor the trial adequately. A risk-based monitoring strategy is developed in this trial, which includes on-site and centralized monitoring, which is more likely than routine visits to all clinical sites and 100% data verification to ensure subject protection and overall study quality. On-site monitoring is an in-person evaluation carried out by the monitor at the sites at which the clinical investigation is being conducted. Centralized monitoring is a remote evaluation carried out at a location other than the sites at which the clinical investigation is being conducted. Key monitoring processes include subject inclusion process; implementation of the inclusion criteria; source data verification; data integrity, etc.

Data management and Statistical methods

Data entry will be conducted by two independent administrators using online electronic CRF for accuracy and consistency. At the end of the study, the database will be locked and analyzed under the agreement of principal investigator and statistician, who are privileged to access the final trial dataset.

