The randomized subjects who take at least one dose of CHM or SMT constitute the full analysis set (FAS) and those who complete all the visits constitute the per-protocol set (PPS). An efficacy assessment will be analyzed using FAS and PPS based on the principle of ITT. Subjects who have taken the CHM and been evaluated the safety at least once constitute the safety set (SS), which is used for safety evaluation. The statistical analysis will be performed using SAS 9.0 software (SAS Institute, Cary, NC, USA) by independent data management committee who are blind to the interventions.

Comparison of the two groups is conducted for the continuous variables with *t*-test and the categorical variables or rates with the chi-square test. The Kaplan-Meier overall survival curves will be generated and tested by log-rank. Cox proportional hazards regression model will be adopted to determine the prognostic factors associated with transplant-free survival. Multivariate logistic regression analyses will be adopted to explore factors associated with the incidence of liver-related complications. Subgroup analyses will be done based on the diagnostic criteria of Asian Pacific Association for the Study of the Liver (APASL) and European Association for the Study of the Liver (EASL) guideline.

The last observation carried forward approach was used for missing values. The statistical significance is defined as a two-sided $P < 0.05$.

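### The safety committee is given no comparison of deaths and adverse events with the concurrent SMT arm, and nothing else in the plan supplies a workable one during the trial

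*Combined protocol and SAP*

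**What the plan says.** Four places in the combined protocol and SAP bear on this.

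- **Safety outcomes.** An independent safety committee analyses adverse events in order to "identify any unexpected adverse events or mortality in the CHM groups". No SMT comparison, expected rate, review schedule or threshold is given. The same paragraph says that "adverse events are also recorded in a predesigned case report form (CRF) through the whole study period", with no limit to one arm.
- **Data management and Statistical methods.** "Subjects who have taken the CHM and been evaluated the safety at least once constitute the safety set (SS), which is used for safety evaluation". SMT patients are therefore outside the safety set. The full analysis set, by contrast, covers treated patients of both arms.
- **Criteria for discontinuing or modifying allocated interventions.** There are two grounds for ending the study. One concerns safety: "The study will end at once if severe adverse events associated with CHM occurs". The other compares the arms: the study also ends if "sufficient evidence indicates that adding CHM is not superior to the SMT group". Neither has a threshold. The second also has no responsible body, no timing and no data source.
- **Opening section.** The only scheduled interim step is an "interim assessment of effective participant numbers around December 2018", which concerns recruitment.

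The only mortality rate in the documents is in Sample size: "our previous results of 30.87% in the SMT group", at 8 weeks.

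**The concern.** If roughly three patients in ten on standard treatment die within 8 weeks, deaths on CHM are certain to occur. A death count becomes unexpected only relative to some reference. The randomised SMT arm is the natural one: same hospitals, same period, same eligibility criteria. The committee's written task does not mention it.

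Without that arm, the committee must rely on an outside rate or on a case-by-case view of whether a death was caused by CHM. Case-by-case attribution is weak when the disease and the treatment can lead to the same event. An outside rate misleads if it does not fit this trial. If SMT mortality here is lower than the outside rate, a real excess on CHM looks ordinary. If it is higher, harmless treatment looks dangerous.

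The fit of the past rate is open to doubt. The trial excludes patients "Complicated by severe cerebral edema, severe infection, type I hepatorenal syndrome (HRS), and gastrointestinal hemorrhage", and the documents do not say whether the earlier SMT patients were selected in the same way. At stake is whether an excess of deaths on CHM would be recognised while patients are still being enrolled and treated.

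**Working it through.** **The plan's own figure.** The 255 per group serves here only to place a halfway look; the point does not depend on it. For 30.87% against 30.87 − 12 = 18.87%, two-sided 0.05 and 80% power, the usual pooled-variance formula gives 203 per group, and 203/0.90 = 226 after 10% attrition. The stated 255 is larger and does not reproduce, but that has no bearing on monitoring.

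**Assumptions for the illustration.** The plan gives none of these to the committee.
- Benchmark for CHM deaths: 30.87% at 8 weeks (Sample size).
- A single look at one-sided 0.025.
- 128 patients per arm with known 8-week status, about half of 255 (255/2 = 127.5).
- True SMT mortality between 20% and 40%.
- True harm on CHM of 10 percentage points, or none.

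**CHM-only rule.** Find the smallest count r with P(X ≥ r) ≤ 0.025 for X ~ Binomial(128, 0.3087). P(X ≥ 50) = 0.030 and P(X ≥ 51) = 0.019, so the rule flags at 51 or more deaths (51/128 = 39.8%). The chance of a flag is P(X ≥ 51) at the true CHM rate.

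**Between-arm rule.** With d the true difference and p̄ the mean of the two rates,

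chance of a flag = Φ[(d − 1.96·SE0)/SE1], SE0 = √(2p̄(1−p̄)/n), SE1 = √([pS(1−pS) + pC(1−pC)]/n).

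For SMT 20% and CHM 30%: SE0 = √(2·0.25·0.75/128) = 0.0541 and SE1 = √((0.16 + 0.21)/128) = 0.0538. Then (0.10 − 0.1061)/0.0538 = −0.113 and Φ = 0.455.

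**Results at 128 per arm**

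| True SMT | True CHM | CHM-only check flags | Between-arm comparison flags |
|---|---|---|---|
| 20% | 30% | 1.1% | 45.5% |
| 25% | 35% | 14.6% | 41.5% |
| 30.87% | 40.87% | 62.6% | 38.5% |
| 35% | 35% (no harm) | 14.6% | 2.5% |
| 40% | 40% (no harm) | 54.8% | 2.5% |

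The first row shows the mechanism. The CHM arm would expect 128 × 0.30 = 38.4 deaths, slightly fewer than the 128 × 0.3087 = 39.5 that the benchmark predicts. The SMT arm would expect 128 × 0.20 = 25.6. The harm is visible only when the two arms are set side by side.

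**Results at 255 per arm** (CHM-only rule: 94 or more deaths). With the 10-point harm, the CHM-only and between-arm figures are 1.1% and 74.3% at SMT 20%, 28.7% and 69.4% at 25%, about 67% each at 28%, and 91.5% and 65.4% at 30.87%. With 40% in both arms, false alarms are 86.2% and 2.5%. This is the end of the trial, when the plan already compares the arms, so the 128-per-arm table is the relevant one.

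**The case against.** The strongest reply has four parts.

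1. **The committee is not barred from SMT data.** A reader might infer that it sees CHM patients alone. The sentence in Safety outcomes says where harm is to be looked for, and adverse event recording is not limited to one arm. This stands: the text is silent on a comparator and does not exclude one. But no comparison is assigned either, and the safety set definition points the same way.

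2. **A comparison with SMT exists.** A reader might infer that the trial has no concurrent yardstick, or that the committee is its only safeguard. The discontinuation criteria contradict both, and an independent research organisation also monitors the protection of participants. This stands too. However, the comparative criterion is framed as lack of superiority rather than harm and cannot be operated as written. The listed key monitoring processes include no review of mortality by arm. The log-rank test has no stated interim use.

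3. **Nobody told the committee to use 30.87%.** Correct. The rate is given for sample size, and both the benchmark and the one-sided 0.025 rule are assumptions made here. Nor do the documents show that SMT mortality in this trial will be lower: the exclusions lower it only if the earlier patients were not selected in the same way.

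4. **A CHM-only check is not always worse.** Correct. If the benchmark is exactly right, it detects the 10-point harm more often, 62.6% against 38.5% at 128 per arm, because it carries no sampling error from a control arm. That advantage requires knowing the SMT rate in advance. If the true rate is lower, detection collapses; if it is higher, false alarms multiply.

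**Conclusion.** The concern holds in this form: the committee is directed to the CHM groups with no assigned comparison with SMT, the safety set contains no SMT patients, and the only comparative stop lacks an owner, timing and boundary. Followed as written, the safety review has no randomised reference for deaths.

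The size depends on the unknown SMT mortality. For a 10-point harm at 128 per arm, a CHM-only check ranges from 1.1% to 62.6% detection as SMT mortality goes from 20% to 30.87%. The between-arm comparison stays between 38.5% and 45.5%. Its false-alarm rate stays at 2.5%, while the CHM-only check reaches 54.8% if both arms are at 40%. These figures rest on the assumed benchmark, single look, significance level and range of rates. They illustrate the problem and do not predict what this committee would do.

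The between-arm figures are modest as well. One halfway look would miss a 10-point harm more often than not. The gain is that the result no longer depends on how well an outside rate fits this trial.

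The documents do not support saying that the committee is blind to SMT outcomes, that no comparison exists anywhere in the plan, or that harm would necessarily go unseen. This should be corrected, but it is a gap in the assignment of a task, not a flaw in the randomised comparison itself.

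**What to change.** - **Safety outcomes:** state that the committee reviews deaths, transplants and serious adverse events in both randomised arms side by side, and judges excess risk on CHM against concurrent SMT.
- **Criteria for discontinuing or modifying allocated interventions:** name the committee as the body that makes the comparison with SMT. The sponsor and the committee should also write down when it is made and what boundary applies; without these, the reworded task still does not ensure detection.
- **Data management and Statistical methods:** extend the safety set to treated patients of both arms, so that it does not contradict the reworded task.

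The cost is a few sentences and no extra patients or visits: the committee exists, and adverse event recording is not limited to one arm. The downside is that by-arm tables must be prepared and kept from the investigators. The plan describes its analysts as blind to the interventions, so someone with access to the allocation must prepare these tables separately.

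### The sample size and its 80% power are set for 8-week mortality, not for the primary outcome, week-12 transplant-free survival, for which the plan gives no rate, effect or power

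*Combined protocol and SAP*

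**What the plan says.** All references are to the combined protocol and SAP.

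- **Sample size:** "The proposed -12% superiority margin of 8-week mortality rate was chosen based on our previous results of 30.87% in the SMT group". With power 0.80 and 10% attrition, "255 subjects are needed for each group to achieve the significance level of 0.05 in assessing the difference between the two groups". No formula, CHM-arm rate or scale for the 12% is given.
- **Outcome measurements, Primary outcome:** "The primary outcome is transplant-free survival at week 12".
- **Outcome measurements, Secondary outcomes:** the list opens "Secondary outcomes include (1) transplant-free survival at week 24" and goes on to MELD, Child-Pugh and quality of life at week 12 and serious complications from week 1 to week 24. Mortality at 8 weeks is not in it.
- **Opening overview:** outcome follow-up comes after the 8-week "observational period until August 30, 2020 for the primary outcome and secondary outcomes". Week 8 and the primary time point are therefore distinct in the plan.
- **Criteria for discontinuing or modifying allocated interventions:** "the final status will be censored in the condition of liver transplantation or the onset of liver cancer". The sentence names no endpoint.
- **Data management and Statistical methods:** comparison of "the categorical variables or rates with the chi-square test"; also, "The Kaplan-Meier overall survival curves will be generated and tested by log-rank". Significance is two-sided at 0.05. Neither test is named as primary.

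**The concern.** A power statement belongs to one endpoint, one time point and one assumed effect. The only one in this plan belongs to an endpoint that the trial does not list. Moving from 8-week mortality to week-12 transplant-free survival changes the follow-up time and possibly the event, because a transplant is not a death. Both changes alter the control rate and the plausible difference, and power depends on both.

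At stake is how the primary result is read against what was planned. If it is not significant, readers will ask which effect the trial was built to detect. The plan answers that only for a different endpoint.

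**Working it through.** **Inputs.** From Sample size: SMT 8-week mortality 0.3087, difference 12% (scale not stated), power 0.80, alpha 0.05, attrition 10%, 255 per group. From Statistical methods: two-sided. Hence z = 1.960 and 0.8416, and (1.960 + 0.8416)² = 7.849.

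**1. Can 255 be reproduced?** Take 12% as absolute (an assumption): p1 = 0.3087, p2 = 0.1887, mean 0.2487.

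- Usual two-proportion formula: n = [1.960·√(2·0.2487·0.7513) + 0.8416·√(0.3087·0.6913 + 0.1887·0.8113)]² / 0.12² = [1.960·0.6113 + 0.8416·0.6054]² / 0.0144 = 202.5, so 203 evaluable. 203/0.9 = 225.6, so **226** per arm.
- With continuity correction: n = (202.5/4)·[1 + √(1 + 4/(202.5·0.12))]² = 218.9, so 219. 219/0.9 = 243.3, so **244** per arm.
- Log-rank formulas at the implied hazard ratio (step 3) give 220 (Schoenfeld) or 232 (Freedman) per arm after attrition.
- Control-rate variance in both arms: n = 2·0.3087·0.6913·7.849/0.0144 = 232.6. Multiplying by 1.10 gives 255.9; dividing by 0.9 gives 258.5. So about **256 to 259** per arm.

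Of the formulas tried at the stated power of 0.80, only the last comes close to 255.

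If 12% is relative, the CHM rate is 0.3087·0.88 = 0.2717. The usual formula then needs about 2,356 evaluable per arm, and 230 analysed would give 14% power. The size of 255 fits only the absolute reading, but the text does not say so.

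**2. Power of 255 per arm for 8-week mortality, absolute reading.** After 10% attrition, 0.9·255 = 229.5, taken as 230. Power is 0.848 with 230 analysed and 0.882 with 255.

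**3. Power for the primary outcome.** No week-12 rate is given, so this step is illustration only. If transplantation counts as an event, the week-12 rate cannot be below 8-week mortality in the same patients; 35% to 50% is assumed here for SMT. Two effects are shown: a fixed 12 points, and the hazard ratio implied by the week-8 rates, ln(1 − 0.1887)/ln(1 − 0.3087) = 0.566, with CHM rate = 1 − (1 − SMT rate)^0.566.

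| Assumed SMT week-12 event rate | Fixed 12 points: power, 230 / 255 analysed | CHM rate at hazard ratio 0.566 | Hazard ratio 0.566: power, 230 / 255 analysed |
|---|---|---|---|
| 35% | 81.2% / 85.0% | 21.7% | 89.1% / 91.9% |
| 40% | 77.7% / 81.8% | 25.1% | 92.8% / 95.0% |
| 45% | 75.3% / 79.5% | 28.7% | 95.4% / 97.0% |
| 50% | 73.8% / 78.1% | 32.5% | 97.1% / 98.2% |

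For a fixed 12 points, power drops below 80% once the SMT rate exceeds about 36.5% (230 analysed) or 44% (255 analysed). At the constant hazard ratio it stays above 80% throughout.

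**The case against.** **The figure of 255 can be explained.** A reader might infer that the plan's own inputs do not give 255 and that the number is a calculation error. The documents do not support that. With z-values rounded to 1.96 and 0.84, the control-variance formula gives 232.4, and 232 × 1.10 = 255.2. That formula is awkward for a superiority comparison, and nothing shows that the sponsor used it. But no formula is named, so an error cannot be asserted. This part of the objection stands, and only the missing formula and scale remain.

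**The trial looks large enough.** A reader might also infer that the trial is underpowered. Nothing shows this. On the stated inputs 255 exceeds both 226 and 244, death is a component of transplant-free survival, and a proportional effect carried to week 12 keeps power high. The shortfalls above require the effect to stay at 12 points while control events rise. This also stands, but it rests on assumptions that the plan does not make, and it does not turn an 8-week calculation into a week-12 one.

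**The primary result can still be interpreted.** An estimate with its confidence interval does not depend on planned power. That is right. What is lost is narrower: the stated 80% cannot be cited for the primary comparison.

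**Margin.** The word might suggest a test against a shifted null hypothesis. The same section speaks of assessing the difference between the groups, and the analysis section describes ordinary tests. Loose wording is the better reading.

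**Censoring.** One could infer that the plan censors transplants in an outcome defined as transplant-free. The sentence names no endpoint, so it shows ambiguity rather than a settled contradiction. It matters here because the event must be defined before it can be powered.

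**Conclusion.** The point holds as a mismatch between the primary outcome and the basis of the sample size. It is not an arithmetic error. That the only power figure concerns 8-week mortality, that this is not a listed outcome, and that no week-12 rate, effect or power is given can all be read directly from the text and need no assumption.

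The size of the consequence is open. On the absolute reading, 255 per arm is ample for 8-week mortality. At week 12 the illustrations fall on both sides of 80%, and which side applies depends on a control rate and an effect scale that the plan leaves out. The 35% to 50% range and the constant hazard ratio are assumptions made for this check, not bounds.

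**What to change.** Keep 255 per arm and rewrite the Sample size section for week-12 transplant-free survival:

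- State the assumed week-12 SMT event rate, from the data behind 30.87% if they reach week 12, and otherwise as a justified assumption with a range.
- Describe 12 percentage points as an absolute target difference, not a superiority margin, and give the resulting CHM rate.
- Name the formula and the single primary test at two-sided 0.05.
- Restate the power of 255 per arm with and without 10% attrition (230 and 255 analysed).
- Reconcile the censoring sentence in the discontinuation criteria with the Primary outcome section, so that it is clear whether transplantation and onset of liver cancer are events or censoring.

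The cost is protocol and SAP wording and one recalculation, with no extra patients. The restated power may fall below 80%, and if the earlier data stop at week 8 the week-12 rate will remain an assumption. Both should be stated openly.

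### Centre is named in neither the allocation nor the tests of a trial at 16 or more hospitals; stratifying both by centre would be a cheap, modest gain in precision, not a correction of bias

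*Combined protocol and SAP*

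**What the plan says.** The opening design description calls this a "This prospective, multi-center, parallel, centrally randomized controlled trial", to run "among 16 tertiary academic hospitals in China". The number of sites may grow: "We will decide whether to expand additional institutions to guarantee adequate enrolments after interim assessment of effective participant numbers around December 2018".

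On allocation, the Randomization section states "The eligible patients will be randomly allocated to the SMT group and CHM group in a 1:1 ratio". It adds that an independent statistician generates the numbers in SAS and that opaque envelopes conceal them. It mentions no centre, stratum, block or minimisation, and does not say how an added hospital gets its allocations.

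On analysis, Data management and Statistical methods compares continuous variables by t-test and "the categorical variables or rates with the chi-square test". For survival, "The Kaplan-Meier overall survival curves will be generated and tested by log-rank". None of these is stratified or adjusted. The Cox and logistic models look for factors related to survival and complications; their covariates are not listed. The only subgroups named are by APASL and EASL criteria.

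**The concern.** Hospital is known for every patient at no cost, and several features of this trial could make outcome differ by hospital:

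- Standard treatment is described by type of measure, which leaves room for local practice.
- Transplantation counts in the primary endpoint, and access to it may vary between sites.
- A central laboratory is named for HBV DNA, endotoxin and cytokines, but none is named for the inputs to MELD and Child-Pugh.
- Hospitals may be added after the December 2018 assessment.

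These are reasons to expect some spread; the documents do not measure it.

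If allocation ignores centre, chance decides how many patients in each arm come from higher- and lower-mortality hospitals. A test that ignores centre leaves that variation in the error. At stake is how precisely the CHM v SMT difference is estimated.

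**Working it through.** **Inputs.** From the Sample size section: control 8-week mortality 30.87%, difference 12 points (so 18.87% under CHM), power 0.80, attrition 10%, 255 per group. Two-sided 0.05 is from the statistical methods, and 16 centres from the design description. Assumed, because the documents give no figure: unequal centre sizes, and normal centre effects on the logit scale with SD 0.3, 0.5 or 0.8. These SDs put control mortality (5th to 95th percentile of hospitals) at about 21-42%, 16-49% and 10-60%.

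**1. The plan's sample size.** The two-proportion formula is n = [1.960·√(2p̄q̄) + 0.842·√(p₁q₁ + p₂q₂)]² / 0.12². With p̄ = 0.2487 it gives n = 203, and 203/0.9 = 226 per group. This is not 255. A margin formula using the control rate in both arms gives (1.960 + 0.842)² × 2 × 0.3087 × 0.6913 / 0.12² = 233; then 233/0.9 = 259, or 233 × 1.1 = 257. Both are within 2% of 255. The difference does not affect what follows, which starts from 255.

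**2. Nominal power.** 255 × 0.9 is about 229 to 230 evaluable per arm. The chi-square test then has power 0.846 to 0.848.

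**3. Simulated operating characteristics.** 60,000 trials per scenario, 458 patients, 16 unequal centres; CMH is the Cochran-Mantel-Haenszel test by centre.

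| Centre SD | Power: unstratified list, chi-square | Power: unstratified list, CMH | Power: stratified list, CMH | Type I: unstratified list, chi-square | Type I: stratified list, chi-square |
|---|---|---|---|---|---|
| 0 | 0.8481 | 0.8349 | 0.8491 | 0.0508 | 0.0503 |
| 0.3 | 0.8479 | 0.8423 | 0.8548 | 0.0495 | 0.0491 |
| 0.5 | 0.8481 | 0.8505 | 0.8622 | 0.0504 | 0.0458 |
| 0.8 | 0.8476 | 0.8682 | 0.8777 | 0.0498 | 0.0401 |

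Changing both list and test gains 0.7, 1.4 and 3.0 points of power at SD 0.3, 0.5 and 0.8, and loses nothing at SD 0. Changing the test alone gives −1.3, −0.6, +0.2 and +2.1 points at SD 0, 0.3, 0.5 and 0.8.

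**4. Chance imbalance in baseline risk.** With an unstratified list its SD is 0.56, 0.91 and 1.37 points. Multiplying by 1.96 gives about 1.1, 1.8 and 2.7 points. With per-centre blocks of 4 or 6 at random, the 95th percentile is about 0.20, 0.33 and 0.50 points. If 10% drop out after allocation, it is about 0.41, 0.66 and 1.04.

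**5. Share of the total error.** The SE of the arm difference is √[(0.3087 × 0.6913 + 0.1887 × 0.8113)/229] = 4.0 points. Centre imbalance contributes (0.56/4.0)² = 2%, (0.91/4.0)² = 5% and (1.37/4.0)² = 12% of that variance.

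**6. MELD and Child-Pugh.** If 5% to 15% of the variance lies between centres (assumed), removing it is worth 1/0.95 = 1.05 to 1/0.85 = 1.18 times the patients.

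**The case against.** The strongest reply has four parts.

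**Silence is not proof.** The document does not say that there is a single list; blocks and strata are simply not reported. Central randomisation neither implies nor excludes stratification by centre, and the Cox model's unlisted covariates could include centre. This stands, so the point must cover both cases. If the list is unstratified, precision is lost; if it is stratified, the plain chi-square does not match the design and becomes conservative. Either way the text needs a change.

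**Validity is not at stake.** A reader might infer that the comparison is biased or the false-positive rate inflated. The documents do not support that: unstratified 1:1 allocation with an unadjusted test holds about 5%, and chance centre imbalance is part of the ordinary sampling error, not an addition to it.

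**The gain is small and rests on assumed heterogeneity.** Power on the stand-in rates already exceeds the planned 0.80. The SD 0.8 case implies wide mortality differences among tertiary hospitals that share one described standard treatment. This stands, and limits the point to a modest improvement.

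**The remedy has a cost.** No placebo is described for the granules or enemas, so staff would see past allocations, and blocks within a centre make later ones partly predictable. Varying block sizes reduces this but does not remove it.

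**Conclusion.** The point holds as a cheap improvement in precision. Against a 12-point target difference, using centre in both list and test cuts chance imbalance from about 1.1-2.7 points to about 0.2-0.5 (95th percentile, before attrition) and adds about 1 to 3 points of power. It reduces imbalance; it would be too strong to say that it abolishes it.

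These sizes rest on three assumptions: a between-centre logit SD of 0.3 to 0.8, an unstratified list as the reading of the present text, and 8-week mortality standing in for week-12 transplant-free survival. If centres are nearly alike, the gain is close to nil but nothing is lost. If the list is in fact stratified by centre, the remaining fault is an unmatched analysis, with type I error about 4.6% at SD 0.5 and 4.0% at SD 0.8.

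**What to change.** **Randomization section.** Have the independent statistician generate the list separately for each centre, in permuted blocks of randomly varying size. Conceal block sizes from the sites and prepare a new list for each added institution. If this is already the practice, say so.

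**Statistical methods.** Use a centre-stratified Cochran-Mantel-Haenszel test for transplant-free survival at weeks 12 and 24, stratify the log-rank test by centre, and include centre in the models for week-12 MELD and Child-Pugh. Pool small centres (for example, those with fewer than about 10 patients) by a rule fixed before unblinding.

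Make the two changes together: a centre-stratified test on an unstratified list can lose about 1 point of power when centres differ little.

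**Cost.** One more parameter in the SAS program, separate lists to manage, a pooling rule, and some predictability of allocation within centres. No more patients are needed. The list has to be settled before the September 2018 start, because allocations already made cannot be restratified.
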